#### 6.3.5.4 Interferon beta (IFN beta)

A 2 mL venous blood sample for the determination of IFN beta in serum will be collected on pre-dose D1 (baseline), D1 (5 minutes after dosing), pre-dose D3 and D7 for hospitalised patients as detailed in the Schedule of Procedures ([Section 6, Table 2](#)). Blood sample preparation and sample storage details are provided in the Laboratory Manual. It is essential that the actual time and date of the collection of each sample is recorded in the sample collection form provided with the laboratory kits and in eCRF.

The post-dose sample taken 5 minutes after study drug administration on D1 must be taken from another extremity than the site where the study drug was administrated.

IFN beta in serum will be analysed centrally by Syrinx Bioanalytics Oy, Turku, Finland.

#### 6.3.5.5 Pharmacogenetics

The genetic sample must be taken for a patient to enter the study. According to the previous Phase III Study (FPCLI002) there may be significant genetic variability in response to the investigational treatment. We specifically aim to investigate whether a specific genetic polymorphism rs9984273, which is the glucocorticoid regulatory motif area of IFN alpha/beta receptor subunit 2, defines responsiveness to treatment, and whether this sub-groups should be a targeted population for the investigational medicinal product.

PIM sample collected pre-dose on D1 will be used for genetic analyses; sample preparation and sample storage details are provided in the Laboratory Manual. Genetic analyses will be done at MediCity Research Laboratory, University of Turku, Turku, Finland.

The samples and data for genetic analysis in this study will be coded. Samples will not carry any personal identifiers. DNA samples will be destroyed 15 years after completion of this study.

#### 6.3.5.6 SARS-CoV-2 viral burden

A 2.5 mL blood sample for SARS-CoV-2 viral burden in serum are collected on pre-dose Day 1 and on Day 3, Day 7, Day 10 and on Day 14 (only for hospitalized patients, if patient's discharge is before D14, the specimen is obtained also on the day of discharge). The date and time of sample collection will be recorded in the-CRF.

### 6.3.5.7 SARS-CoV-2 variants

A nasopharyngeal swab is taken on pre-dose Day 1 for central analysis of variants of SARS-CoV-2.

### 6.3.6 Lung X-ray/CT scan

For the purpose of diagnostic accuracy, the study will utilize only documentation of lung X-ray/CT scan performed as part of standard clinical care; separate X-ray/CT scans are not performed for study purpose. No separate imaging manual exists for the Study, and images will not be collected.

## 6.4 Post-Discharge Assessments

Patients will be contacted at D14, D28 (if discharged; assessment window of +/- 3 days permitted, but with exact assessments for D14 and D28 conditions) and D90 (if discharged; assessment window of +/- 1 week permitted) to assess for health status, including mortality. At D14 and D28 the patient will be assessed on changes in the concomitant medications and on possible adverse events. On D90 only survival and hospital status will be collected. At the time of enrolment, subjects will be asked to provide at least two methods of contact, as well as contact information for a caregiver, to facilitate contact at Day 90. Patients who cannot be reached by phone will be mailed a follow up letter. The information is sought through records if the patient cannot be contacted.

Please see section 6.3. for patients that have been discharged from the hospital but are re-admitted due to COVID-19 before D28 to the study site.

## 6.5 Withdrawal Prior to Day 28

For patients withdrawing from the study, procedures for the last day of study involvement should be followed.

In the case of an ongoing AE, appropriate safety evaluations and/or additional tests may be performed at any time when clinically indicated at the discretion of the attending physician or Investigator, until resolution or Day 28, whichever is first. Any ongoing AEs should be followed up to resolution or Day 28, whichever is the sooner.

If the patient refuses to have any of the above assessments, or if the patient is lost to follow-up, then this should be noted in the e-CRF. If a patient is lost to follow-up, wherever possible, mortality data will be sought from alternative sources, such as the patient's local physician or available national databases and all data obtained reported as SAEs.

## 6.6 Safety Variables

### 6.6.1 Adverse Events

#### 6.6.1.1 Collection of Adverse Events

It is the responsibility of the Investigator to collect all AEs (both serious and non-serious) derived by observation, by spontaneous unsolicited reports of patients, and, where appropriate, by routine open questioning, e.g., "How have you felt since I last saw you?"

#### 6.6.1.2 Definitions

Definitions of AEs and SAEs and their documentation and reporting within this study follow International Conference on Harmonisation (ICH) Good Clinical Practice, European Union, and national regulations and requirements.

An AE is defined as any untoward medical occurrence that occurs in a patient or clinical investigation subject administered a pharmaceutical product, and which does not necessarily have to have a causal relationship with this treatment. An AE can therefore be any unfavourable and unintended sign (including an abnormal laboratory finding), symptom or disease temporally associated with the use of an investigational product, whether or not considered related to the product.

All AEs up to D28 are collected. AEs occurring after D28 should be reported to the Sponsor if the Investigator considers there is a causal relationship with the study drug. All AEs up to D90, which lead to death, are reported as SAEs. Concomitant illnesses, which existed before entry into the study, will not be considered AEs unless there is any deterioration from baseline that is considered clinically relevant or significant during treatment or follow-up period until D28. All AEs must be documented, regardless of the source of identification (e.g., physical examination, laboratory assessment, ECG, reported by patient).

Pre-existing conditions will be recorded in the e-CRF on the Medical History or appropriate page. A TEAE (Treatment-Emerged Adverse Event) is defined as an AE that begins or that worsens in severity after at least one dose of study drug has been administered up to D28.

See 6.1 for the schedule of collection of adverse events

### 6.6.1.3 Assessment of Adverse Events

It is recognised that the patient population in the hospital will experience a number of common aberrations in laboratory values, signs and symptoms due to the severity of their underlying disease and the impact of standard therapies. These will not necessarily constitute an AE unless they require intervention, lead to discontinuation of blinded study drug or are considered to be of concern in the Investigator's clinical judgement.

Each AE will be assessed by the Investigator with regard to the following categories:

#### 6.6.1.3.1 Seriousness

An SAE is defined as any untoward medical occurrence that at any dose:

- Results in death
- Is life-threatening. This means that the patient is at risk of death at the time of the event. It does not mean that the event hypothetically might have caused death if it were more severe
- Requires inpatient hospitalisation or prolongation of existing hospitalisation
- Results in persistent or significant disability or incapacity
- Is a congenital anomaly or birth defect
- Is an important medical event that may not be immediately life-threatening or result in death or hospitalisation but that may jeopardise the patient or require intervention to prevent one of the above outcomes. Examples of such events are intensive treatment in an emergency room or at home for allergic bronchospasm; blood dyscrasias or convulsions that do not result in hospitalisation; or development of drug dependency or drug abuse

Medical and scientific judgment should be exercised in deciding whether a case is serious and whether expedited reporting is appropriate. However, all deaths up to D90 will be reported as a SAE.

“At any dose” does not imply that the patient is receiving study treatment at the time of the event. Study drug doses may have been given during treatment cycles or interrupted temporarily prior to the onset of the SAE, but may have contributed to the event.

#### 6.6.1.3.2 *Intensity*

Investigator will be responsible for the assessment of severity, using the categories of mild, moderate or severe to describe each AE as:

- **Mild:** Does not interfere with patient’s usual function
- **Moderate:** Interferes to some extent with patient’s usual function
- **Severe:** Interferes significantly with patient’s usual function

Note the distinction between serious and severe AEs. **Severe** is a measure of intensity whereas an event must meet one of the criteria for serious events listed in [Section 6.6.1.3.1](#) to be considered **serious**; thus, a **severe** reaction is not necessarily a **serious** reaction. For example, a headache may be severe in intensity, but would not be classified as serious unless it met one of the criteria for serious events listed in [Section 6.6.1.3.1](#).

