## 2.4 Dexamethasone

### 2.4.1 Clinical safety experience of Dexamethasone

I.V dexamethasone is recommended therapy for hospitalized patients with hypoxemia who are receiving oxygen through a high-flow device, or non-invasive ventilation, or invasive ventilation. It is also recommended for patients receiving increasing amounts of supplemental oxygen therapy (<https://www.covid19treatmentguidelines.nih.gov/therapies/immunomodulators/corticosteroids/>). It has been proposed that the potent anti-inflammatory effects of corticosteroids might prevent or mitigate the deleterious systemic inflammatory effects in patients with severe form of COVID-19.

The incidence of side effects associated with the use of dexamethasone generally correlates with dosage, timing of administration, and duration of treatment. The most commonly occurring side effects of dexamethasone have included a wide range of psychiatric reactions, psychotic reactions, behavioural disturbances, irritability, anxiety, sleep disturbances and cognitive dysfunction including confusion and amnesia, decreased blood eosinophils and lymphocytes, increased infection susceptibility, masking of infection signs, aggravated infection, and fungal infections of mucous membranes and the skin. In adults the frequency of severe reactions has been estimated to be 5-6%.

In this study, 6 mg IV doses of dexamethasone will be administered for 6 days. Adverse reactions associated with the use of glucocorticoids are usually dependent on the dose and the duration of the

treatment. Treatment duration of 6 days is relatively short, and the occurrence of the above-mentioned reactions associated with long-term use is unlikely.

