Phase III clinical studies (INTEREST and MR11A8-2) and phase I clinical study (FP1CLI011) in healthy volunteers did not identify any major safety risks for FP-1201-lyo. A decrease in IL-6 IL-8 and IFN-gamma values was observed in patients treated with FP-1201-lyo, a finding that was similar to those found in a placebo group (Ranieri et al. 2020). Fever was the most common AE in phase III studies, and all healthy volunteers in the study FP1CLI011 experienced fever as a response to the treatment. The pyrogenic effect is characteristic for IFN beta-1a as well as for other type I IFNs. In healthy volunteers, the body temperature characteristically reached 38–39°C (axillary) 1-2 hours after the FP-1201-lyo administration, and this elevation persisted for around 2 hours (all treated with antipyretic analgesics). The temperature elevations vary substantially among individuals. IFN beta-1a induced fever responds to antipyretic analgesic drugs, which are recommended to decrease (or prevent) the flu-like symptoms associated with IFN beta-1a administration. Serious adverse reactions possibly related to IFN beta-1a reported more than once in phase III clinical trials, include two cases of increased transaminases, two cases of thrombocytopenia, three cases of hypertension, and two cases of rhabdomyolysis. The available information suggests that the present study's risk/benefit ratio is favourable.

Investigating the effect of IFN beta-1a to prevent ARDS in viral pneumonia (and particularly SARS-CoV-2) is especially intriguing because of the potential beneficial effects of IFN beta-1a in direct viral defense, association of type I IFN deficiency with worse outcomes in COVID-19 (Hadjadj et al 2020, Zhang et al. 2020), and the induction of CD73-mediated preventive effects on endothelial barrier function and pulmonary capillary leak. The current study aims to detect the benefit of IFN beta-1a in clinical outcome measures (WHO 9-point ordinal scale), reduced need of mechanical ventilation, mortality and development of organ failure and ARDS versus the current standard of care for COVID-19. Dexamethasone was chosen as the comparator arm to align with treatment guidelines for hospitalized COVID-19 patients requiring supplemental oxygen. The rationale underlying the current design is provided below. Safety of both treatment arms will be assessed equally.

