#### 6.6.1.3.4 *Adverse events related to laboratory assessments*

Abnormal laboratory findings (e.g., biochemistry, haematology, urinalysis) or other abnormal assessments (e.g., vital signs) that are judged by the Investigator as clinically significant will, if certain requirements are met, be recorded as AEs or SAEs. Clinically significant abnormal laboratory findings or other abnormal assessments that meet the definition of an AE or SAE and are detected during the study, or are present at baseline and significantly worsen following the start of the study, will be reported as AEs or SAEs.

The Investigator will exercise their medical and scientific judgment in deciding whether an abnormal laboratory finding or other abnormal assessment is clinically significant and as such an AE.

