### 7.6.1 Adverse Events

AEs and SAEs will be coded using the current version of Medical Dictionary for Regulatory Activities (MedDRA) and will be classified by system organ classes and preferred terms. In the event that intensity or relationship of an AE to the study drug is missing, a worst-case scenario will prevail (severe in intensity or probably related). Only TEAEs (AEs that occur after the first study drug administration, that were not pre-existing or that increased in intensity) will be included in the summary tables. Counting will be performed for patients and events separately. Patients experiencing the same event more than once will have that event counted once within the corresponding system organ class and with a unique preferred term. All AEs will be included in the data listings. Listings of SAEs, of AEs leading to study drug withdrawal and of AEs leading to death will also be provided.

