Collected data will be listed and presented descriptively only. Following summary tables will be presented in support to patient listings:

- Study termination and primary reason for discontinuation
- Patient disposition
- Demographic characteristics
- Study drug exposure
- Summary of Treatment-Emergent Adverse Events (TEAEs)
- Deaths

Summary tables regarding adverse events (AEs) will be presented at least by system organ class (SOC), preferred term (PT) and severity including number of patients and events for all TEAEs, severe TEAEs, serious TEAEs, drug-related TEAEs, serious drug-related TEAEs and TEAEs leading to study drug discontinuation.

Based on the data from only 5 individual subjects some of the tables may be left out from the final table package due the sparsity of the table to be meaningful to produce, for example, deaths will not be tabulated if all study participants are alive.

7 Hardware and software

Tables and patient data listings are produced with SAS® 9.4 TS1M6 for Windows (SAS Institute Inc., Cary, NC, USA).

8 References

1. HIBISCUS Study Protocol, version 4.0 (27th September 2021), Faron Pharmaceuticals Ltd.

9 Appendices

- A. HIBISCUS updated sample size calculation, final version (1st April 2021).

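### Adverse-event intensity is graded by function alone, so a symptom-free laboratory abnormality is mild at any value, and its worsening from baseline may not count as treatment-emergent

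*Protocol*

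**What the plan says.** Protocol section 6.6.1.3.2 has the investigator give each AE one of three intensities. The lowest is "Does not interfere with patient’s usual function" and the highest is "Interferes significantly with patient’s usual function". Usual function is not defined for a hospitalised patient on oxygen, and no numeric or laboratory criterion appears here or elsewhere in either document.

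Section 6.6.1.3.4 makes a laboratory finding an AE when the investigator judges it clinically significant. It adds that such findings which "are present at baseline and significantly worsen following the start of the study, will be reported as AEs or SAEs". That rule does not mention function.

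Two passages define a TEAE. Section 6.6.1.2 calls it "an AE that begins or that worsens in severity after at least one dose of study drug", up to Day 28. Section 7.6.1 restricts the tables to AEs after the first dose "that were not pre-existing or that increased in intensity) will be included in the summary tables". AEs are recorded from the signing of consent (section 6.6.1.4), so a laboratory AE can exist before dosing.

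SAP section 6 states: "Summary tables regarding adverse events (AEs) will be presented at least by system organ class (SOC), preferred term (PT) and severity". It names separate summaries for all, severe, serious, drug-related and serious drug-related TEAEs, and for those leading to discontinuation of study drug.

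**The concern.** Safety and tolerability is the first primary objective (Protocol section 3.1), and the severity breakdown and severe-TEAE table are among the few summaries the SAP keeps. Several effects the protocol names for IFN beta-1a show up as measured values: anaemia, lower platelets and raised hepatic enzymes (section 2.3.4), and a neutrophil fall that section 2.6 says must be monitored. A scale that looks only at function cannot separate a trivial from an extreme value of any of these while the patient has no symptoms.

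The SAP has nothing that would make up for this. Chemistry and haematology appear only as listings (SAP 9.1), and the tabulation plan (SAP 9.2) has no laboratory table, although Protocol section 7.5.3 planned descriptive laboratory statistics by arm.

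The second problem is one of fit between rules. The laboratory rule recognises worsening by clinical significance; the TEAE rules recognise it by a change of grade. If the grade cannot move, a real worsening may not be counted.

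**Working it through.** The point rests on definitions and there is no stated figure to reproduce. The check takes symptom-free laboratory events through the rules as written.

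| Case | An AE? (6.6.1.3.4) | TEAE under 6.6.1.2? | In the tables under 7.6.1? | Severe-TEAE table? |
|---|---|---|---|---|
| A. Abnormality starts after dosing | Yes, if judged clinically significant | Yes, it begins after a dose | Yes, not pre-existing | No, graded mild |
| B. Abnormal at baseline, not recorded as an AE, then significantly worse | Yes | Yes, if the AE is taken to begin after dosing | Unclear: the abnormality is pre-existing and the grade is still mild | No |
| C. Recorded as an AE between consent and first dose, then worse | Yes | No, unless the worsening is entered as a new AE | No, unless the worsening is entered as a new AE | No |
| D. Any of these, meeting a seriousness criterion (6.6.1.3.1) | Yes, as a serious AE | As for A, B or C | As for A, B or C; if treatment-emergent, in the serious table whatever the grade | No |

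The severe-TEAE table is therefore closed to all four cases while the event stays symptom-free. Loss from every TEAE table is clear only in case C, and case B is ambiguous.

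**Missing grades.** Section 7.6.1 sets a missing intensity to severe. This does not close the gap, and it produces an odd contrast: an ungraded symptom-free laboratory AE is tabulated as severe, while the same event graded as instructed is mild.

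**Serious reactions named in Protocol section 2.6.** The section lists "two cases of increased transaminases, two cases of thrombocytopenia, three cases of hypertension, and two cases of rhabdomyolysis" among the serious, possibly related reactions reported more than once:

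- total: 2 + 2 + 3 + 2 = 9 cases;
- purely laboratory (transaminases, platelets): 2 + 2 = 4;
- hypertension, a vital sign: 3;
- rhabdomyolysis, a clinical diagnosis with a laboratory component: 2.

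All 9 were serious, so similar treatment-emergent events would reach the serious table under case D.

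**Illustrative numbers at the planned size.** Section 2.3.4 gives rates in IFN beta-1a patients from the two earlier phase III trials in ARDS. Applied to 70 patients in the IFN arm:

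- anaemia: 70 × 0.111 = 7.8;
- platelet decrease: 70 × 0.061 = 4.3;
- raised hepatic enzymes: 70 × 0.068 = 4.8.

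These are expected events of all grades. The documents give neither the symptom-free share nor the share that a value-based scale would call severe. The number missing from the severe table could therefore be anything from 0 up to about 8, 4 and 5 respectively.

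**The case against.** A reader might infer that the laboratory risks of IFN beta-1a are hidden from the TEAE tables altogether. The documents do not support that. A laboratory AE with onset after dosing is a TEAE at any intensity and is tabulated by organ class and preferred term. The serious, drug-related and discontinuation tables do not use intensity. Seriousness is judged separately, and section 6.6.1.3.1 gives blood dyscrasias as an example of an important medical event. Certain loss needs case C, which is confined to the interval between consent and a first dose due within 48 hours of arrival at hospital. Individual laboratory values are also listed.

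A reader might also infer that the severity comparison is tilted towards IFN beta-1a, because its risks are measured values and those of dexamethasone, such as "psychiatric reactions, psychotic reactions, behavioural disturbances, irritability, anxiety, sleep disturbances and cognitive dysfunction", are functional. Some such effect is plausible, but the documents do not establish it:

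- The same sentence in section 2.4.1 goes on to lower eosinophil and lymphocyte counts, which are laboratory effects of dexamethasone.
- Fever, not a laboratory finding, was the most common AE in both phase III trials (12.5% against 7.9% on placebo, and 34.7% against 6.8%).
- The 6.8% rate for hepatic enzymes applied to both groups.
- The neutrophil fall was seen in healthy volunteers and not in the severely ill patients of the phase III trials.

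Finally, the investigator owns the grade, and section 6.6.1.3 warns that abnormal laboratory values are common in this population.

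These arguments limit the point but do not remove it. Section 6.6.1.3.2 itself says that severe and serious are different things, so the serious table is no substitute for a severity grade. Listings of raw values are no substitute either.

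**Conclusion.** The point holds in a limited form. Under the plan as written, a symptom-free laboratory AE is mild at any value, so it cannot enter the severe-TEAE table or be told apart in the severity breakdown. The TEAE wording in sections 6.6.1.2 and 7.6.1 also does not fit the laboratory rule in section 6.6.1.3.4. A laboratory AE recorded before the first dose that worsens without symptoms can miss the TEAE tables, and the status of a baseline abnormality not previously recorded as an AE is unclear.

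This assumes that sites apply the scale literally, that the event stays symptom-free and, for case C, that the worsening is not entered as a new AE. No bias between arms can be given a size. The practical effect on this trial is small: SAP section 2 reports five patients enrolled and dosed, and SAP section 6 plans descriptive reporting with no formal hypotheses. The weakness would have mattered more at the planned 140 patients. It is worth correcting because the correction is cheap.

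**What to change.** 1. In Protocol section 6.6.1.3.2, keep the investigator's functional grade for symptoms. For laboratory AEs, add a grade based on the measured value, using the Table 3 variables, the local reference ranges and one standard published toxicity scale named in advance, with a stated mapping to mild, moderate and severe.
2. In SAP section 6, say that the value-based grade is used for laboratory AEs in the severity breakdown and the severe-TEAE table.
3. In Protocol sections 6.6.1.2 and 7.6.1, state that significant worsening from the pre-dose value, as described in section 6.6.1.3.4, counts as treatment-emergent whether or not the functional grade changes and whether or not the abnormality was recorded as an AE before dosing.

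The laboratory values are collected and the reference ranges supplied to the sponsor under section 6.3.4.1, so no new sampling is needed. The cost is a short text change, plus programming to link AE records to laboratory values. If the change were made only in the SAP, the derived grade could differ from the investigator's e-CRF grade, so the SAP should say how both are shown. More events will be reported as severe or treatment-emergent in a population where abnormal values are common, and the report should say so.
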